possibly, probably or definitely attributed to ALRN-6924. Grading of AEs will be defined by the NCI Common Terminology Criteria for Adverse Events (CTCAE) version 4.03 (See [Appendix O](#)). As drug-related AEs Grade ≥ 2 occurred in DL-4A (fatigue) and in DL-3B (neutropenia), subsequent dose escalations with DL-5A and DL-4B continued using modified Fibonacci sequence (i.e., 67%, 50%, 40%, and 33%).

Escalation to the next dose level within each DR may proceed in the absence of DLT at the completion of Cycle 1 (treatment cycle = 28 days for DR-A, DR-A-2 and 21 days for DR-B). Escalation to the next dose level within each DR as well as the DR and DL for the EXP cohorts will be decided by a Safety Review Committee (SRC), consisting of the Principal Investigators and Sponsor's Medical Monitor, which will review all available safety information from all patients. As two DLTs have occurred in DR-7A (hypotension and hepatobiliary laboratory abnormalities), there will be no further escalation in DR-A. A new modified infusion regimen was tested (DR-A-2) starting at DR-7A-2. As two DLTs have occurred in DR-7A-2 (anemia and neutropenia), there will be no further escalation in DR-A-2.

Based on review of available safety and PK data during this and other studies with ALRN-6924, dose escalation or modification steps may be adjusted (i.e. increased or decreased) by the SRC to limit the number of patients exposed to sub-therapeutic dose levels as well as to ensure patients' safety.

Within each Dose Regimen cohort:

- If no DLT is observed in a cohort, the subsequent patient group will be enrolled at the next planned dose level of that dose regimen.
- If a DLT is observed in ≥ 2 of 3 patients at any dose level, no further dose escalation will occur in that DR, and the current dose will be defined as the maximum administered dose (MAD).
- If a DLT is observed in 1 of 3 patients in a cohort at any dose level, then up to 6 patients total will be enrolled in the same DR at that dose level. If a DLT is observed in 2 or more patients in the expanded cohort, then no further dose escalation will occur, and the current dose will be defined as the MAD, unless the SRC decides that there is sufficient clinical uncertainty about the DLTs that warrants the enrollment of up to 6 additional patients. In the event of additionally enrolled patients, if a DLT is observed in 33% or more DLT-evaluable patients in the entire cohort, then no further dose escalation will occur, and the current dose will be defined as the MAD for the dosing regimen under consideration.
- After the MAD is defined, either the previously administered lower dose will be expanded to a total of 6 patients, or an intermediate dose (between the MAD and the previous dose level) will be investigated in a total of 6 patients. The highest dose tolerated in at least 5 of 6 patients (i.e. $<33\%$ of DLT-evaluable patients experiencing a DLT) will be defined as the MTD or OBD. Additional patients may be added to further explore the MTD or OBD prior to expansion.

The SRC may hold the dose (e.g., stop dose escalation) at their discretion and enroll additional patients until sufficient safety data are obtained to determine escalation of the current dose level or to confirm a certain dose level as an MTD or OBD.

Dose Level and Dose Regimen – Phase 2a dose expansions

Based on the safety, efficacy and PK/PD profile of ALRN-6924 from the dose escalation portion of the study as well as data from other clinical trials and preclinical data, three dosing regimens of ALRN-6924 administered as single agent therapy (DR-A, DR-B, DR-C) will be tested in Phase 2a EXP in PTCL to determine the optimal dosing regimen.

For patients with MDM2 amplified or MDM2/CDK4 co-amplified solid tumors, patients will receive ALRN-6924 in combination with palbociclib. Palbociclib will be administered at an oral dose of 100 mg daily (Days 1-21) in combination with ALRN-6924, which will be administered at 3.1 mg/kg on Days 1, 8, and 15 of a 28-day cycle (or as otherwise determined during the safety run-in period for this cohort).

The decision to begin palbociclib below the approved dose level of 125 mg is based on the frequency of required

dose reductions, often due to neutropenia. The SRC may consider escalating to the approved palbociclib dose, if palbociclib-related toxicities are not prohibitive and patient benefit is expected to outweigh risk.

Dose Level and Dose Regimen – Phase 2a dose expansions:

Treatment Regimen	Drug and Dose Level	Infusion Days	Infusion Time	Additional notes
DR-A	ALRN-6924 3.1 mg/kg	1, 8, 15 of a 28-day cycle	1 hour (± 15 min)	At the end of the infusion, IV fluids (saline) or oral fluids (500 mL – 1000 mL) should be administered, unless clinically contraindicated.
DR-B	ALRN-6924 2.7 mg/kg	1, 4, 8, 11 of a 21-day cycle	1 hour (± 15 min)	At the end of the infusion, IV fluids (saline) or oral fluids (500 mL – 1000 mL) should be administered, unless clinically contraindicated.
DR-C	ALRN-6924 3.1 mg/kg [If 3.1 mg/kg is not well tolerated, lower doses may be tested starting at dose levels of -25%]	1, 3, 5 of a 21-day cycle	1 hour (± 15 min)	At the end of the infusion, IV fluids (saline) or oral fluids (500 mL – 1000 mL) should be administered, unless clinically contraindicated.
Combination with palbociclib	ALRN-6924 3.1 mg/kg [If 3.1 mg/kg is not well tolerated, up to two dose reductions of 25% may be tested]	1, 8, 15 of a 28-day cycle	1 hour (± 15 min)	At the end of the infusion, IV fluids (saline) or oral fluids (500 mL – 1000 mL) should be administered, unless clinically contraindicated.
	Palbociclib 100 mg [If 100 mg is not well tolerated, a reduced dose of 75 mg may be tested.]	1-21 of a 28-day cycle	Oral	Palbociclib should be administered with food. On days when both drugs are administered (Days 1, 8, and 15 of each cycle), palbociclib should be administered at least 6 hours after the infusion of ALRN-6924.

Intra-patient Dose Escalation – Phase 1 Dose Escalation

A patient's dose may be increased to that of a cohort that completed the first cycle without dose-limiting toxicity in $\geq 33\%$ of DLT-evaluable patients and that has not exceeded the MTD. Intra-patient dose escalations will be allowed provided that the patient completed at least two treatment cycles and did not experience study medication-related toxicity greater than Grade 2 (except for alopecia, electrolyte disturbances responsive to correction within 24 hours,

diarrhea, nausea, fatigue and vomiting that responds to standard medical care). Approval for intra-patient dose escalation must be obtained from the Medical Monitor.

Dose Modifications – Phase 1 dose escalation (ALRN-6924 administered as single agent therapy)

In the event a Grade 4 AE considered related to ALRN-6924 is observed, the patient must be discontinued from the study. Exceptions include Grade 4 neutropenia lasting <3 days, and emesis, diarrhea or electrolyte abnormalities that resolve within 2 days on optimum treatment. For these exceptions, treatment may be delayed for up to 2 weeks to allow resolution of the toxicity (i.e., return to Grade ≤ 1 or baseline), followed by re-treatment at a reduced dose. Two dose reductions are permitted, a third dose reduction will require evidence of clinical benefit and approval by the Medical Monitor. Relevant labs should be repeated as medically indicated.

In the event a Grade 3 AE considered related to ALRN-6924 is observed (exceptions are Grade 3 fatigue, nausea, emesis, diarrhea or clinically insignificant electrolyte abnormalities that resolve within 2 days on optimum treatment), treatment may be delayed for up to 2 weeks to allow resolution of the toxicity, followed by re-treatment at a reduced dose. Two dose reductions are permitted, a third dose reduction will require evidence of clinical benefit and approval by the Medical Monitor. Relevant labs should be repeated as medically indicated.

Following related Grade 3 and Grade 4 AEs (as permitted), the dose for re-treatment will be reduced by 25% intervals (e.g., if the dose is 3.1 mg/kg, the dose will be reduced sequentially to 2.3 mg/kg and 1.7 mg/kg).

For other clinically significant AEs, treatment may be delayed by up to 2 weeks to allow for the resolution of AEs to an acceptable level, and a dose reduction may be made as described above at the discretion of the Investigator in consultation with Sponsor's Medical Monitor. If a patient experiences multiple AEs, decisions on dosing delay or dose reduction will be based on the most severe AE. Any patient who experiences recurrent, clinically significant AEs after one dose reduction may undergo one additional dose reduction. Patients who continue to experience clinically significant AEs after a 2-week delay or the maximum allowed number of dose reductions will be discontinued from study treatment.

Adverse events considered for dose reduction should not include events assessed by the Investigator as exclusively related to underlying disease or other medical condition or concomitant treatment. A patient who experiences an AE considered related to ALRN-6924 that does not meet the requirement for discontinuation may continue on study if the patient is receiving clinical benefit and/or the Investigator feels continued participation is in the best interest of the patient. In such cases, at the Investigator's discretion and in agreement with Sponsor's Medical Monitor, the dose for a patient may be reduced as described above.

A patient who experiences a DLT must continue treatment at a reduced dose level, or discontinue ALRN-6924 treatment (if Grade 4 related AE), as described above at the discretion of the Investigator and in agreement with Sponsor's Medical Monitor until disease progression or unacceptable toxicity. Once the dose has been reduced for a patient, it may not be re-escalated.

Dose Modifications – Phase 2a dose expansions in PTCL (ALRN-6924 administered as single agent therapy)

In the event a non-hematologic Grade 4 AE considered related to ALRN-6924 is observed, the patient must be discontinued from the study. Exceptions include emesis, diarrhea or electrolyte abnormalities that resolve within 2 days on optimum treatment. For these exceptions, treatment may be delayed for up to 2 weeks to allow resolution of the toxicity (i.e., return to Grade ≤ 1 or baseline), followed by re-treatment at a reduced dose. Relevant labs should be repeated as medically indicated.

In the event a non-hematologic Grade 3 AE considered related to ALRN-6924 is observed (exceptions are Grade 3 fatigue, nausea, emesis, diarrhea or clinically insignificant electrolyte abnormalities that resolve within 2 days on optimum treatment), treatment may be delayed for up to 2 weeks to allow resolution of the toxicity, followed by re-treatment at a reduced dose. Relevant labs should be repeated as medically indicated.

For hematologic toxicities, patients must discontinue treatment with ALRN-6924 if

- Neutrophil counts $< 0.5 \times 10^9/L$ for > 5 days, or
- Platelet counts $< 10 \times 10^9/L$, or
- Hemoglobin $< 6 \text{ g/dL}$ (despite RBC transfusion or Erythropoiesis-Stimulating Agent (ESA) administration)

Patients interrupt treatment if

- Neutrophil counts $< 0.5 \times 10^9/L$ for ≤ 5 days, or
- Platelet counts $< 25 \times 10^9/L$ and $> 10 \times 10^9/L$, or
- Hemoglobin $< 8 \text{ g/dL}$ and $> 6 \text{ g/dL}$

After resolution of hematologic toxicity (i.e., return to Grade ≤ 1 or baseline), patients may continue at a reduced dose. Relevant labs should be repeated as medically indicated.

Following related Grade 3 and Grade 4 AEs (as permitted), the dose for re-treatment will be reduced by 25% intervals (e.g., if the dose is 3.1 mg/kg, the dose will be reduced sequentially to 2.3 mg/kg and 1.7 mg/kg). Two dose reductions are permitted, a third dose reduction will require evidence of clinical benefit and approval by the Medical Monitor.

Dose Modifications – Phase 2a dose expansion in MDM2 amplified or MDM2/CDK4 co-amplified solid tumors (ALRN-6924 plus palbociclib)

Dose modifications of ALRN-6924 will be as described above for the Phase 1 dose escalation. Dose modifications of palbociclib are to be made in accordance with the current approved US prescribing information. In the event that palbociclib administration must be discontinued, the patient may continue to receive ALRN-6924 as a study participant until a criterion for treatment discontinuation has been met. However, if discontinuation of ALRN-6924 is required, patients will be considered to have discontinued study treatment. These patients may continue to receive palbociclib treatment at the investigator's discretion.

Dose Limiting Toxicity Definition during Phase 1 Dose Escalation

A DLT will be defined as any Grade ≥ 3 AE that is considered possibly, probably, or definitely related to the study drug, with the following exceptions: (1) for fatigue, nausea, emesis, diarrhea or mucositis, only Grade ≥ 3 AE that do not respond within 48 hours to standard supportive/pharmacological treatment will be considered DLT; (2) for electrolyte imbalances, only Grade ≥ 3 AE that do not respond to correction within 24 hours will be considered DLT; (3) for infusion reactions, only a Grade 3 reaction which caused hospitalization or Grade 4 will be considered DLT. In addition, specific hematologic DLTs are defined as:

- Thrombocytopenia – Grade 4 of any duration, Grade 3 for ≥ 7 days, or Grade 3 associated with clinically significant bleeding
- Neutropenia – Grade 4 for ≥ 3 days, or any Grade ≥ 3 febrile neutropenia

The above criteria will be used to make individual patient determinations regarding dose reductions, interruptions or discontinuation throughout the course of the trial, but DLTs occurring during Cycle 1 will be used to inform safety and tolerability assessments for dose escalation decisions.

Study Drug Administration

ALRN-6924 will be administered as an IV infusion as follows:

Phase 1 Dose Escalation (ALRN-6924 administered as single agent therapy):

- Dose Levels 1 and 2 Dose Regimen A on Days 1, 8, and 15 of each 28-day cycle (1 hour infusion)
- Dose Levels 3 and beyond as follows –
 - Dose Regimen A on Days 1, 8, and 15 in a 28-day cycle (1 hour infusion)

- Dose Regimen B on Days 1 and 4, 8 and 11 in a 21-day cycle (1 hour infusion)
- Dose Regimen A-2 on Days 1, 8, and 15 in a 28-day cycle (2 hour infusion) [starting with Dose Level 7]

Patients who remain on study treatment for 2 years or longer may have their dosing frequency reduced, at the discretion of the investigator (i.e., Days 1 and 15 of a 28-day cycle (DR-A) or Days 1 and 8 of a 21-day cycle (DR-B). In the event that disease control is not maintained, the original dosing schedule may be resumed.

Phase 2a Dose Expansion in PTCL (ALRN-6924 administered as single agent therapy):

- Dose Regimen A 3.1 mg/kg on Days 1, 8, and 15 in a 28-day cycle (1 hour infusion)
- Dose Regimen B 2.7 mg/kg on Days 1 and 4, 8 and 11 in a 21-day cycle (1 hour infusion)
- Dose Regimen C 3.1 mg/kg on Days 1, 3 and 5 in a 21-day cycle (1 hour infusion). [If 3.1 mg/kg is not well tolerated, lower doses may be tested starting at dose levels of -25%]

Phase 2a Dose Expansion in MDM2 amplified or MDM2/CDK4 co-amplified solid tumors (ALRN-6924 plus palbociclib):

- ALRN-6924: 3.1 mg/kg (1 hour infusion) on Days 1, 8, and 15 in a 28-day cycle plus palbociclib: 100 mg per day orally on Days 1-21 in the same 28-day cycle. It is recommended that palbociclib be administered with food. On days when both drugs are administered (Days 1, 8, and 15 of each cycle), palbociclib should be administered at least 6 hours after the infusion of ALRN-6924.

Following the administration of each dose of ALRN-6924, patients must receive 500 to 1000 mL of IV or oral fluids, unless clinically contraindicated.

Statistical Methods

For each phase of study, results will be summarized by dose level and regimen. Tabulations will be produced for appropriate demographic and baseline clinical characteristics, efficacy, pharmacokinetic, and safety parameters. For categorical variables, summary tabulations of the number and percentage of patients within each category of the parameter will be presented. For continuous variables, the number of patients, mean, median, standard deviation, minimum, and maximum values will be presented. Time-to-event data will be summarized using Kaplan-Meier methodology using 25th, 50th (median), and 75th percentiles with associated 2-sided 95% confidence intervals. Graphical displays will be presented, as appropriate. Results will be evaluated for all patients.

TABLE OF CONTENTS

INVESTIGATOR'S SIGNATURE PAGE.....	2
ALRN-6924-1-01 SYNOPSIS.....	3
TABLE OF CONTENTS.....	21
LIST OF TABLES.....	25
LIST OF FIGURES	25
ACRONYM LIST.....	26
1 BACKGROUND AND STUDY RATIONALE	29
1.1 Therapeutic Rationale for Inhibiting MDM2/MDMX to Restore p53 Activity	29
1.2 Stapled Peptide Technology	30
1.3 ALRN-6924.....	30
1.4 Nonclinical Experience with ALRN-6924	30
1.4.1 Pharmacology.....	30
1.4.2 Toxicology and Nonclinical Safety.....	31
1.4.3 Pharmacokinetics and Absorption, Distribution, Metabolism and Excretion	33
1.4.4 ALRN-6924 Administered in Combination with Palbociclib	34
1.5 Clinical Experience with ALRN-6924	41
1.6 Clinical Experience with Palbociclib	41
2 STUDY OBJECTIVES	42
2.1 Phase 1 Dose Escalation (ALRN-6924 administered as single agent therapy)	42
2.1.1 Primary Objectives.....	42
2.1.2 Secondary Objectives	42
2.1.3 Exploratory Objectives.....	42
2.2 Phase 2a Dose Expansion (ALRN-6924 administered as single agent therapy)	42
2.2.1 Primary Objectives.....	42
2.2.2 Secondary Objectives	42
2.2.3 Exploratory Objectives.....	43
2.3 Phase 2a Dose Expansion in MDM2 Amplified or MDM2/CDK4 Co-amplified Solid Tumors (ALRN-6924 plus palbociclib)	43
2.3.1 Primary Objectives.....	43
2.3.2 Secondary Objectives	43
2.3.3 Exploratory Objective	43
3 INVESTIGATIONAL PLAN	44

3.1	Study Rationale	44
3.2	Study Overview.....	44
3.2.1	Pharmacokinetic, Pharmacodynamic, and Clinical Activity Assessments.....	47
3.3	Number of Patients and Centers.....	49
3.4	Duration of Study	49
4	PATIENT POPULATION	50
4.1	Inclusion Criteria – Phase 1 dose escalation (ALRN-6924 administered as single agent therapy)	50

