This study consists of a Phase 1 Dose Escalation Phase (DEP) and a Phase 2a Dose Expansion Phase (EXP). The DEP is a “3+3” dose escalation design to establish the MTD or the OBD of ALRN-6924. The EXP will enroll up to 5 distinct groups of patients with specific solid tumors and/or lymphomas to further investigate the clinical safety profile and potential efficacy of ALRN-6924 at the MTD, OBD, or in alternate dosing regimens.

In the Phase 2a EXP, peripheral T-cell lymphoma (PTCL) has been selected as one of the diseases to be further studied in up to 3 cohorts to identify the optimal dosing regimen.

Another Phase 2a EXP group will include patients with MDM2 amplified or MDM2/CDK4 co-amplified solid tumors who will receive ALRN-6924 in combination with palbociclib. As these agents have not previously been co-administered, a safety run-in of 6-8 patients will first be enrolled and evaluated by the sponsor and the primary investigators before further patients are permitted to enroll. Patients will receive ALRN-6924 at the previously determined recommended Phase 2 dose for the once-weekly administration schedule (3.1 mg/kg on Days 1, 8, and 15) and palbociclib at an oral dose of 100 mg daily for 21 days (one dose level below the approved oral dose of 125 mg) in a 28-day cycle. Doses of ALRN-6924 and palbociclib may be adjusted for safety or tolerability prior to enrolment of additional patients into this EXP group.

Treatment of patients in the dose escalation and the dose expansion phases of the study will continue until

unacceptable toxicity, patient or physician decision to discontinue therapy or disease progression that is either symptomatic, rapidly progressive, requires urgent intervention, or is associated with a decline in performance status.

TP53 Status Determination and Tumor Sampling Requirements

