2. STUDY DESIGN

2.1. BRIEF DESCRIPTION

This is a Phase 1/2a open-label, multi-center, dose-escalation study designed to evaluate the safety, tolerability, PK, PD, and antitumor effects of ALRN-6924 in subjects with advanced solid tumors or lymphomas with WT TP53.

The Phase 1 portion of the study, referred to as the dose escalation phase (DEP), is a “3+3” dose escalation design to establish the MTD and OBD of ALRN-6924. Dose cohorts are delineated in the study protocol.

Two regimens are explored in the Phase 1 portion of the study:

- Dose Regimen A: once weekly for 3 consecutive weeks (Days 1, 8, and 15 of a 28-day cycle)
- Dose Regimen B: twice weekly for 2 consecutive weeks (Days 1, 4, 8, and 11 of a 21-day cycle)

The Phase 2a portion of the study, referred to as the dose expansion phase (EXP), will enroll up to 5 distinct groups of subjects with specific solid tumors and/or lymphomas to further investigate the clinical safety profile and potential efficacy of ALRN-6924 at the MTD or OBD. A third dosing regimen, Dose Regimen C, will also be explored during the EXP. Subjects assigned to this regimen will receive ALRN-6924 on days 1, 3, and 5 of a 21-day cycle.

Treatment of subjects in the dose escalation and the dose expansion phases of the study will continue until documentation of disease progression, unacceptable toxicity, or subject or physician decision to discontinue therapy. Subjects receiving clinical benefit may continue on study after a discussion between the Principle Investigator and Medical Monitor.

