8. SAFETY ANALYSES

8.1. STUDY TREATMENT AND EXTENT OF EXPOSURE

The ALRN-6924 administration profile will be summarized with respect to treatment duration (Treatment duration (days) = last treatment date - first treatment date + 1), number of infusions, total ALRN-6924 dose received (mg), average dose per cycle, number of cycles, number of subjects with dose modification(s), and reason for dose modification(s).

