8.3. ADVERSE EVENTS

Treatment-emergent adverse events (TEAEs) are defined as AEs that are newly occurring or worsening on or after the date of the first dose of ALRN-6924. Reported AE terms will be coded using MedDRA version 19.1 or later.

The number and percent of subjects, and the number of events where relevant, will be summarized by SOC and PT for the following categories of TEAEs:

- All TEAEs
- Grade 3 or higher CTCAE grade TEAEs
- Related TEAEs defined as at least possibly related, as delineated by the investigator, or missing
- Serious TEAEs

- Serious related TEAEs
- TEAEs leading to discontinuation of study drug
- TEAEs leading to death

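### The Phase 1 SAP's average dose per cycle and crude TEAE percentages are not comparable between 28-day and 21-day regimens with open-ended treatment; dose per week, delays and exposure-adjusted AE rates should be added

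*Protocol*

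**What the plan says.** SAP 3.1 limits the plan to Phase 1 and announces a separate plan for Phase 2a. It tabulates by dose cohort within regimen, by regimen and over all subjects, with DR-A and DR-A-2 combined.

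SAP 8.1 summarizes treatment duration, defined as "Treatment duration (days) = last treatment date - first treatment date + 1", and the number of infusions. It then lists "total ALRN-6924 dose received (mg), average dose per cycle, number of cycles", followed by the number of subjects with dose modifications and the reasons.

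For treatment-emergent events, SAP 8.3 states: "The number and percent of subjects, and the number of events where relevant, will be summarized by SOC and PT". Its TEAE definition has a start but no end. The protocol synopsis (Statistical Methods) gives only the general rule for categorical variables, "summary tabulations of the number and percentage of patients within each category of the parameter will be presented".

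The design facts that bear on these summaries are:

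- Dose is calculated from body weight at the start of each cycle (Protocol 5.3).
- DR-A and DR-A-2 are given on Days 1, 8 and 15 of 28 days, and DR-B on Days 1, 4, 8 and 11 of 21 days (Protocol 5.3).
- Treatment has no set number of cycles (Protocol 5.3).
- Toxicity delays of up to 2 weeks are allowed (Protocol 5.8.1).
- AE reporting ends 30 days after the last dose, or earlier if new anticancer therapy starts (Protocol 8.2).

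**The concern.** Safety and tolerability are a primary Phase 1 objective (Protocol 2.1.1), and readers will set the DR-A and DR-B columns side by side. Two of the planned summaries do not support that reading.

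First, the only dose-rate measure uses the cycle as its unit of time, and that unit differs between regimens. The overall column then averages the two units together. Total dose in mg also mixes body weight with dose. No table shows how much of the planned dose was delivered on time.

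Second, a crude percentage of subjects with an event grows with time under observation, which here follows time on treatment. If one regimen is taken for longer, perhaps because it works better or is easier to stay on, its percentages rise for that reason alone.

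**Working it through.** The plan states no expected AE rate or dose intensity, so it has no figure of its own to reproduce.

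**Schedule.** Infusions per week = infusions per cycle ÷ (cycle days ÷ 7).

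- DR-A and DR-A-2: 3 ÷ 4 = 0.75.
- DR-B: 4 ÷ 3 = 1.33.
- At equal mg/kg per infusion, DR-B over DR-A is 4 ÷ 3 = 1.33 per cycle, but 1.333 ÷ 0.75 = 1.78 per week.

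**Delay at unchanged dose.** Take four cycles with one 14-day delay before the last cycle and full dose throughout. Average dose per cycle does not change. Relative dose intensity, counting each cycle at its full length, is:

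- DR-A: 112 ÷ (112 + 14) = 88.9%.
- DR-B: 84 ÷ (84 + 14) = 85.7%.

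The delay does move SAP treatment duration:

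- DR-A: from 3 × 28 + 15 = 99 to 113 days.
- DR-B: from 3 × 21 + 11 = 74 to 88 days.

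So a delay can be worked out from duration together with cycles or infusions, but it is not reported as such.

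**Crude TEAE percentage.** Assume a constant hazard h per month, exponential time on treatment with mean m months, and the full 30-day AE window (one month) after the last dose. With μ = 1/m,

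incidence = 1 − exp(−h) × μ/(μ + h).

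For h = 0.10:

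- m = 2: 1 − 0.9048 × 0.5/0.6 = 24.6%.
- m = 5: 1 − 0.9048 × 0.2/0.3 = 39.7%.

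Over a range of hazards:

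| h per month | m = 2 | m = 5 |
|---|---|---|
| 0.05 | 1 − 0.9512 × 0.5/0.55 = 13.5% | 1 − 0.9512 × 0.2/0.25 = 23.9% |
| 0.10 | 24.6% | 39.7% |
| 0.20 | 1 − 0.8187 × 0.5/0.7 = 41.5% | 1 − 0.8187 × 0.2/0.4 = 59.1% |

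In every row the two regimens are equally toxic per month.

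**Can the order reverse?** Use fixed treatment times and incidence = 1 − exp(−h × (months + 1)). The milder regimen has h = 0.10 for 6 months: 1 − exp(−0.7) = 50.3%. The comparator is stopped at 2 months.

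- Twice the hazard: 1 − exp(−0.6) = 45.1%, the wrong order.
- Three times the hazard: 1 − exp(−0.9) = 59.3%, the right order.

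Events confined to Cycle 1 would show no effect of later treatment.

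**The case against.** The plan gives more than these two summaries. Duration, infusions, cycles, dose modifications with reasons, event counts where relevant and full listings are all planned, and every table is split by dose cohort within regimen. A reader might infer that treatment delays vanish from the output. They do not, as the shift from 99 to 113 days shows. What is missing is a direct summary. Duration also reflects when patients stop treatment, and SAP 8.1 does not say whether a delay counts as a dose modification, although Protocol 5.8.1 treats delays under that heading.

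Protocol 5.8.1 also follows most delays for related Grade 3 and permitted Grade 4 events with a reduced dose, which dose per cycle would register. A delay at full dose remains possible for other clinically significant events, where reduction is discretionary. Long delays at full dose in every cycle would be an extreme case that the section largely rules out for toxicity.

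A reader might also infer that the regimen taken longest will look the most toxic. That does not follow: the ranking depends on hazards, durations and the timing of events, none of which the documents give.

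Dose escalation rests on Cycle 1 DLTs within each regimen, not on whole-period percentages. That is correct. However, the Cycle 1 window is itself 28 or 21 days, and Protocol 5.9.3 reopens tolerability when DLT-type toxicities appear in later cycles.

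Finally, one might carry the point to the PTCL expansion, which is "to be further studied in up to 3 cohorts to identify the optimal dosing regimen". SAP 8.1 and 8.3 do not govern Phase 2a, and its analysis plan is not among the documents, so no flaw can be asserted there.

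**Conclusion.** The point holds for the Phase 1 SAP as an inexpensive improvement to reporting. It shows no error in the escalation rules. Average dose per cycle understates the DR-B to DR-A contrast (1.33 against 1.78 at equal mg/kg per infusion) and does not respond to a delay at full dose. That part is arithmetic on the stated schedules.

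The AE part is conditional. Crude percentages can differ by about 10 to 18 percentage points at identical toxicity over assumed hazards of 0.05 to 0.20 per month and mean treatment of 2 versus 5 months. Other assumptions give other gaps, or none. The calculation uses the full 30-day window; earlier subsequent therapy would shorten it.

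The expansion doses show why the Phase 2a plan should carry the same measures. DR-A and DR-C are both 3 × 3.1 = 9.3 mg/kg per cycle, but 9.3 ÷ 4 = 2.325 and 9.3 ÷ 3 = 3.10 mg/kg per week, a 33% difference. This illustrates what that plan needs to cover and is not a finding against it.

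**What to change.** **SAP 8.1.** Replace or supplement average dose per cycle with delivered dose intensity in mg/kg/week and relative dose intensity (delivered over planned). Add the number and length of delays, and say whether a delay counts as a dose modification.

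- Compute the planned dose from each patient's assigned dose and schedule at the time. Permitted intra-patient escalation (Protocol 5.7.3) and the permitted reduction in dosing frequency after 2 years (Protocol 5.3) are then not read as excess or poor delivery.
- Run the time denominator to the end of the last scheduled cycle. The SAP's duration stops at the last infusion: four DR-A cycles on schedule give 99 days rather than 112.

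**SAP 8.3.** Keep the crude percentages. Add TEAE rates per patient-month at risk, including the 30-day window, and incidence in the first 84 days (3 × 28 = 4 × 21). Show how many patients were still under AE observation at Day 84, because a common window does not equalize follow-up for those who stop early.

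**Phase 2a analysis plan.** Carry over the same measures, including DR-C at 3 infusions per 21 days.

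The cost is SAP wording and a few table columns, derived from dosing dates, weights and AE dates already collected. Nothing in treatment or data collection changes.
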